9.4. Relative Dose Intensity

Relative dose intensity is the dose intensity divided by the planned dose intensity.

For AG-221, the planned dose intensity is based on the assigned dose each time.

For LDAC, subjects randomized to LDAC treatment option will receive cytarabine 20 mg SC BID for the first 10 days of each every 28-day treatment cycle. Therefore, the planned dose intensity is 14.3 mg/day throughout the study;

For azacitidine, subjects in this group will receive 75 $\text{mg}/\text{m}^2/\text{day}$ for 7 days of each 28-day treatment cycle, so the planned dose intensity is 18.75 $\text{mg}/\text{m}^2/\text{day}$;

For IDAC, subjects randomized to IDAC treatment option will receive cytarabine 0.5 to 1.5 g/m^2 IV for the first 3 to 6 days of each 28-day treatment cycle. The dosing schedule is flexible with each site, so for calculation purpose, prior to the final analysis, the planned dose intensity for one specific cycle will be calculated in the following way:

Planned dose intensity = [dose administered (g/m^2) x actual duration (Days)]/28, which equals to X.X $\text{g}/\text{m}^2/\text{day}$.

Relative dose intensity for all four drugs mentioned above will be categorized into < 75%, 75% to < 90%, and $\geq 90\%$, and frequency counts will be provided by treatment group.

9.5. Average Daily Dose

Average daily dose during treatment is defined as the cumulative dose divided by number of days dosed. A single average value will be computed for each subject, overall and within each cycle, and then the descriptive statistics will be computed for each treatment group. Average daily dose will be summarized for the prescribed daily dose (mg/day for AG221 and LDAC; g/m²/day for IDAC; and mg/m²/day for azacitidine), and the total daily dose.

9.6. Dose Modification

This part does not apply to BSC only group.

The number of subjects who have at least one dose modification, number of dose modifications per subject, and reasons for dose modifications will be summarized by treatment group. Details of dose adjustments will be provided in a by subject listing.

According to protocol, under specific circumstances, AG-221 dose may increase for augmenting treatment responses. Number of subjects who undergo dose escalation, number of subjects who have dose modification after dose escalation will be summarized. Reasons for dose modifications after dose escalations will also be summarized.

9.7. Compliance

Overall and by cycle study medication compliance, which is measured by relative dose intensity (see Section 9.4 for details), will be summarised by treatment.

10. EFFICACY ANALYSIS

All efficacy analysis will be performed on the ITT population unless otherwise specified. Key efficacy analyses will also be performed on the mITT population as supportive evidence and to assess the robustness of the efficacy findings. Subjects will be analyzed according to randomized treatment group. Statistical comparisons will be made between AG-221 and CCR overall and by pre-selected CCR therapy whenever applicable.

All statistical tests will be two-sided at the significance level of 0.05, and the corresponding two-sided p-values and two-sided 95% confidence interval (CI) for intended point estimates will be reported, unless specified otherwise.

10.1. Multiplicity

In order to perform hypothesis testing on multiple endpoints while controlling the overall Type I error rate, a closed, sequential testing approach is proposed to test endpoints in a pre-specified order. The primary efficacy endpoint of OS will be tested first at a two-sided significance level of 0.05. If superiority of AG-221 is demonstrated in OS, then the first key secondary endpoints of overall response rate (ORR) will be tested next. The second key secondary endpoint of the event-free survival (EFS) will be tested only if the test results for both OS and ORR are significant each at a two-sided 0.05 significance level. The interim superiority analysis adopts Lan-DeMets version of the O'Brien-Fleming alpha spending function to control the overall Type I error rate. The alpha spending completed in the interim analysis is further detailed in Section 12.2 of this document. The multiplicity strategy is applied to hypothesis tests between AG-221 and CCR overall group only.

10.2. Analysis of Primary Efficacy Endpoint

The primary efficacy endpoint of OS is defined as the time between randomization and death from any cause. Subjects who are alive or whose death status is unknown will be censored at the last date known alive on or before data cutoff date. The OS period in months is calculated as (the earlier of death date/the last date known alive and cutoff date – date of randomization + 1)/30.4375. For subjects who were known to be alive and in the study at data cut-off (were not lost to follow-up, and had not withdrawn consent), the last known-to-be-alive date is set to be the data cut-off date.

The analysis of the primary endpoint will be based on the ITT population. Subjects will be analyzed as they were randomized, regardless of the actual treatment received. The survival distribution of OS will be estimated using Kaplan-Meier (KM) method. The 25th percentile, median and 75th percentile of OS including two-sided 95% CI for each treatment arm will be provided, and their differences with 95% CIs between two arms will be calculated using Kosorok's method. KM curves will be provided by treatment arm in figures.

A stratified log-rank test will provide the pivotal p-value for the comparison of the two survival curves of AG-221 vs. CCR arm overall. Hazard ratio and its two-sided 95% CI will be estimated from a stratified Cox proportional hazards regression model. The stratification factors are:

- Prior intensive therapy for AML: yes versus no
- Primary refractory: yes versus no
- Prior allogeneic HSCT for AML: yes versus no

They are assessed by investigators and captured both in the IVRS system at the time of screening phase and in the CRF. In case the site made a stratification error at the time of screening/randomization, stratification errors are corrected in the CRF. Stratified analysis will use stratification factors taken from the CRF. If data does not converge in the stratified analysis due to small sample size in stratum or if there are less than 40 subjects in a stratum, the stratification factor leads to least subjects will be dropped from the model.

Reasons for censoring (e.g., lost to follow-up, withdrew consent, alive at data cut-off, Discontinuation due to other reasons) will be summarized (n, percent) for the OS endpoint.

An unstratified log-rank analysis and Cox regression will be considered as supporting analyses. Stratified analyses based on IVRS stratification factors will be included as a sensitivity analysis.

The analyses on the primary endpoint will be repeated for AG-221 versus BSC Only, Azacitidine + BSC, LDAC + BSC, IDAC + BSC individually by pre-selected CCR therapy.

In addition, sensitivity analyses will be done in the following ways:

1. Analysis of OS using mITT population;
2. Censoring subjects at the time of transplantation after study treatments;
3. Censoring subjects at the start date of any subsequent AML therapy;
4. Censoring subjects at the start date of any subsequent therapy for diseases other than AML excluding the use of hydroxyurea;
5. Censoring subjects for subsequent treatment of AG-221 after initial CCRs;
6. Inverse Probability of Censoring Weighted (IPCW) method censoring subjects at off-protocol AG-221;
7. IPCW method censoring subjects at any subsequent AML therapies if applicable;
8. Rank Preserving Structural Failure Time (RPSFT) model adjusting the confounding effect of off-protocol AG-221 if applicable;
9. Regression based imputation method adjusting subsequent AML therapies if applicable.

At the final analysis, the assumption of proportional hazards will be tested using a time-dependent Cox model with categorical variables for survival time (e.g., 0 – 3 months, 3 – 6 months, 6 – 9 months, etc.) and with following covariates:

- Treatment
- Prior intensive therapy for AML (yes, no) from CRF;
- Prior refractory (yes, no) from CRF;
- Prior stem cell transplants for AML (yes, no) from CRF;

If the model does not converge due to small sample size, the covariate leads to least subjects will be dropped from the model. If a stratification factor covariate has less than 40 subjects in one of its levels across treatment groups, then this factor will not be used in stratified analysis; A statistically significant estimation of any of these survival time categories indicates that the proportional hazard assumption is violated. A figure of smoothed hazard function over time will give an instinct idea of hazard trend over time.

If proportional hazard assumption is violated, the following sensitivity analyses will be conducted using ITT population:

1. Restricted mean survival time will be calculated between AG-221 and CCR arms;
2. Piecewise cox regression will provide hazard estimates for every 3 months;
3. Piecewise cox regression will provide hazard estimates for every 6 months;
4. In the presence of non-proportional and early OS separation, a generalized Wilcoxon test will be utilized to compare survival curves.

A number of subgroups analyses will also be carried out. For details see Section 10.4.

Additionally, the primary endpoint will be repeated for a dose level group analysis of AG-221 subjects who had at least one dose > 100mg during the study versus those who received only dose \leq 100mg.

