### 9.6.1. Primary Efficacy Analysis

The primary efficacy endpoint of OS is defined as the time between randomization and death from any cause. All subjects will be followed until drop-out, death or End of Trial. Drop-out may be due to withdrawal of consent from further data collection or loss to follow-up. Subjects who drop-out or are alive at End of Trial will have their OS times censored at the time of last contact, as appropriate.

The analysis of the primary endpoint will use the stratified log-rank test in the ITT population. This test will provide the pivotal p-value summarizing the comparison of the two OS curves of AG-221 and CCRs. Subjects will be analyzed as they were randomized, regardless of the actual treatment received. The stratification used for the log-rank test will be the same stratification used for randomization. The corresponding stratified Cox proportional hazards regression model with treatment as the only term will be used to estimate the hazard ratio and a 95% confidence interval.

The assumption of proportional hazards will be tested by a time-dependent Cox model with the interaction of treatment and time. A significant interaction indicates that the proportional hazard assumption is violated. Under such circumstance, restricted mean survival time and piecewise Cox regression will be adopted to estimate treatment effect. Generalized Wilcoxon test will be utilized as a sensitivity analysis when treatment difference occurs early rather than late during the Follow-up period.

In order to assess the impact of subsequent enasidenib treatment in the CCR arm, sensitivity analyses of OS will be conducted following ICH E9 (R1) addendum, in which strategies to address intercurrent events are described. To be specific, Hypothetical Strategy, eg, regression-based imputation method (Luo, 2016) and Rank Preserve Structure Failure Time model (Robins, 1991), Principal Stratum Strategy, eg, Inverse Probability of Censoring Weighted method (Robins, 2000), and While on Treatment Strategy to censor subjects at the time of crossover will be adopted to provide supporting evidence when appropriate. In addition, to assess the impact of subsequent transplantation, a sensitivity analysis of OS will be conducted in which subjects who have subsequent transplantation will be censored at the time of transplantation after study treatments.

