13. CHANGES TO THE STATISTICAL ANALYSES SECTION OF THE PROTOCOL

Additional analysis of the Transfusion Independence of subjects will be conducted, which is not mentioned in the Protocol. For details see Section [10.3.2.8](#) of this SAP.

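### SAP 10.2 checks proportional hazards on survival-time categories, without the protocol's treatment-by-time interaction, and treats any one significant category as a violation

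*SAP*

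**What the plan says.** Protocol 9.6.1: "The assumption of proportional hazards will be tested by a time-dependent Cox model with the interaction of treatment and time". Its decision rule follows: "A significant interaction indicates that the proportional hazard assumption is violated".

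SAP 10.2 keeps the model label but changes the content. Proportional hazards will be tested "using a time-dependent Cox model with categorical variables for survival time", with 3-month bands given only as an example and the list left open. The covariates named are treatment and three baseline factors; no product of treatment and time appears. The decision rule is: "A statistically significant estimation of any of these survival time categories indicates that the proportional hazard assumption is violated". SAP section 10 sets every test at two-sided 0.05, and no joint test or adjustment is given for this one.

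If violation is declared, SAP 10.2 calls for restricted mean survival time (RMST) and piecewise Cox models cut every 3 and every 6 months. The remaining analysis carries a second condition: "In the presence of non-proportional and early OS separation, a generalized Wilcoxon test will be utilized to compare survival curves".

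SAP section 13, which lists departures from the protocol, has one entry: "Additional analysis of the Transfusion Independence of subjects will be conducted, which is not mentioned in the Protocol".

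**The concern.** The protocol asks whether the treatment effect changes over time. The SAP rule, as worded, asks whether the time bands themselves have an effect. In a Cox model that question belongs to the unspecified baseline hazard and says nothing about proportionality. If treatment-by-band terms were intended, calling violation when any one of them is significant is a multiple-testing rule whose error rate depends on a number of bands that the SAP does not fix.

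The stakes are limited but real. The primary result does not depend on this check: "A stratified log-rank test will provide the pivotal p-value for the comparison of the two survival curves", whatever the check shows. Kaplan-Meier curves and the smoothed hazard figure are also produced in any case. But the check switches the planned supportive OS analyses on or off, and a declared violation casts doubt on the single HR reported beside the p-value. The question could well arise here: the protocol's amendment justifications say that response to AG-221 may often be late, and that control subjects may go on to commercial AG-221.

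**Working it through.** **Design inputs (SAP 4.4; Protocol 9.3 and Length of Study).** 316 subjects 1:1; CCR median OS 5.6 months, AG-221 median 8 months, so HR = 5.6/8 = 0.70; exponential OS; accrual 3 per month for 12 months, then 9 per month; drop-out about 9%; 250 deaths, expected at about 42 + 7 = 49 months.

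**Reproducing the plan's figure.** The documents give no operating figure for the proportional-hazards check, so the event count is verified instead. Schoenfeld: 4(1.960 + 0.842)²/(ln 0.7)² gives 247 deaths. Freedman gives 253. The stated 250 lies between them, with 80.5% power by Schoenfeld.

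**Reading 1: time bands as main effects.** For a death at time t in subject i, with band indicators I_j(t), the partial-likelihood term is

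exp(βx_i + Σγ_j I_j(t)) / Σ_{l at risk} exp(βx_l + Σγ_j I_j(t)).

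I_j(t) depends on t only, so exp(Σγ_j I_j(t)) is common to numerator and denominator and cancels. The γ_j cannot be estimated. As an illustration, in one simulated trial with 6 bands the log partial likelihood was -1218.8737 with all band effects at 0, and the same with effects (0, 1, -2, 3, -1, 2).

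**Reading 2: treatment-by-band contrasts.** Estimate a log-HR b_j in each 3-month band (last band open-ended), compare each later band with the first by z_j = (b_j - b_1)/√(v_j + v_1), and declare violation if any |z_j| > 1.96. Were the m contrasts independent, the false-violation rate would be 1 - 0.95^m. They share the first band, so simulation is needed. HR is held at exactly 0.7, without baseline covariates.

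- Run A: 20,000 trials, analysis at the 250th death (mean month 48.9), 9.3% dropping out before death.
- Run B: 4,000 trials per setting, fixed cut-off at 49 months, drop-out taken as 9% per year (about 255 deaths).

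| Bands (contrasts) | 1 - 0.95^m | Any-one, A | Any-one, B | Joint test, A | Joint test, B |
|---|---|---|---|---|---|
| 3 (2) | 9.75% | - | 9.0% | - | 5.2% |
| 4 (3) | 14.3% | 12.7% | 12.6% | 4.5% | 4.4% |
| 5 (4) | 18.5% | 16.3% | 15.3% | 4.2% | 3.7% |
| 6 (5) | 22.6% | 19.4% | 19.7% | 3.7% | 3.9% |
| 8 (7) | 30.2% | 21.0% | 21.7% | 2.3% | 2.6% |

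A single treatment × log(time) term gave 4.8% in run A.

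**Why many bands are a problem even for a joint test.** Mean deaths per band with 8 bands in run A: 83.8, 58.6, 39.5, 25.5, 16.3, 10.3, 6.4, 9.3. The last three hold about 6 to 10 deaths each, and some band is inestimable in about 16% of trials (17% in a repeat run). With 4 bands the last holds 25.5 + 16.3 + 10.3 + 6.4 + 9.3 = 67.8.

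**Missed violations.** Assume a delayed effect: HR 1.0 to month 3, then 0.55 (8,000 trials). Detection: log(time) 44.9%; joint test 43.9% (4 bands) and 27.2% (8); any-one rule 68.6% (4) and 72.1% (8). A repeat run gave 44% for log(time) and 69-73% for the any-one rule.

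**The case against.** The strongest reply is that this is incomplete wording and not a changed method. The SAP keeps the protocol's label for the model, the protocol left the form of time to be detailed, and the piecewise Cox analyses use matching 3-month intervals, so treatment-by-band terms are the natural meaning. The literal reading would fail on the first program run and could not quietly mislead anyone. A drafting loss is indeed the likely explanation. But that leads only to reading 2, where the any-one rule and the open list of bands remain.

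A second reply is that a false alarm merely adds sensitivity analyses to the report, and that a stricter test would miss more real departures. Both facts stand: nothing confirmatory is touched, and under the assumed delayed effect detection falls from 69-72% to 45%. Yet the higher figure is bought with a false-alarm rate of 13-21% at 4 to 8 bands, and a false alarm wrongly states that the assumption behind the primary HR has failed. If missing a departure is the greater worry, the answer is to report the supportive analyses unconditionally, with no declaration of violation attached.

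Third, the sizes rest on assumptions. The number of bands is not given; with 3 bands the rate is 9.0%. The runs carry no baseline covariates, and the size and timing of the delayed effect are illustrative. The 8-band figures are the least firm because of the inestimable bands. The direction is the same for every choice of three or more bands tried.

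**Conclusion.** The concern holds: the rule is wrong as written, not merely short of detail. Taken literally it yields no test. Taken as treatment-by-band contrasts, it declares a violation in about 13% (4 bands) to 21% (8 bands) of trials in which the HR is exactly constant at 0.7, against a nominal 5%. The departure from the protocol is undeclared.

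The consequence is confined to which supportive OS analyses are run and how the primary HR is described. The pivotal p-value, its alpha, the event target and the HR estimate do not change. It should be corrected, but it does not threaten the trial's primary conclusion. The false-alarm figures assume the design's exponential OS, 3-month bands with an open last band, and no baseline covariates.

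**What to change.** Restore the treatment-by-time interaction in SAP 10.2 and pre-specify one test at two-sided 0.05. Either of these would do:

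- a single treatment × log(time) term; or
- one joint Wald test on k - 1 degrees of freedom of all treatment-by-band terms, with bands fixed in advance so that each has enough deaths. For example, 0-3, 3-6, 6-9 and over 9 months hold about 84, 59, 40 and 68 deaths under the design.

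Use the same stratification factors that remain in the primary OS model after the SAP's sparse-data rule, under which "the stratification factor leads to least subjects will be dropped from the model". If a different test from the protocol's is intended, list it in SAP section 13.

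Optionally, report RMST and the piecewise HRs whatever the test shows, since even a correct 5% test misses more than half of the delayed effect assumed above (45% detected).

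The cost is SAP wording and a few lines of code, with no new data. The trade-off is lower detection than the any-one rule, which unconditional reporting largely offsets.

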### 9.3. Sample Size and Power Considerations

The equality of overall survival curves will be compared between the AG-221 and CCR treatment arms using a stratified log-rank test. Subjects will be randomized to receive AG-221 treatment or a CCR treatment option pre-selected by the investigator in a 1:1 ratio. Assuming a median OS of 5.6 months in the CCR treatment arm (Roboz, 2014), a median OS of 8 months in the AG-221 treatment arm (42.9% improvement), and a drop-out rate of approximately 9%, this design requires 250 deaths and 316 subjects (158 per treatment arm) to be randomized in order to achieve 80% power to detect a constant hazard ratio (HR) of 0.7 and demonstrate a statistically significant difference in OS at a Type I error rate of 0.05 (two-sided). It is assumed that the OS distribution is exponential with a constant failure rate and that accrual rate is 3 subjects per month for the first 12 months and 9 subjects per month afterwards. The interim analysis for superiority will be conducted at 65% information (ie, 163 deaths) based on Lan-DeMets version of the O'Brien-Fleming alpha spending function.

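### The generalized Wilcoxon sensitivity test of OS is run only when the observed curves separate early, so its p-value, when reported, does not have a 5% false-positive rate

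*SAP*

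**What the plan says.** The primary OS comparison is clear. SAP 10.2: "A stratified log-rank test will provide the pivotal p-value for the comparison of the two survival curves of AG-221 vs. CCR arm overall".

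The same section then plans a proportional-hazards check from a time-dependent Cox model with "categorical variables for survival time (e.g., 0 – 3 months, 3 – 6 months, 6 – 9 months, etc". Its decision rule is: "A statistically significant estimation of any of these survival time categories indicates that the proportional hazard assumption is violated". What follows depends on that result: "If proportional hazard assumption is violated, the following sensitivity analyses will be conducted using ITT population". Item 4 of the list adds a second condition: "In the presence of non-proportional and early OS separation, a generalized Wilcoxon test will be utilized to compare survival curves".

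Protocol 9.6.1 has its own version: "Generalized Wilcoxon test will be utilized as a sensitivity analysis when treatment difference occurs early rather than late during the Follow-up period". There, non-proportionality is judged by a treatment-by-time interaction, and it is not clear that the Wilcoxon sentence requires that interaction to be significant.

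Neither document gives a time point, size or direction for an early difference. Neither changes how the Wilcoxon p-value is to be read, so the opening rule of SAP 10 applies: "All statistical tests will be two-sided at the significance level of 0.05".

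**The concern.** A generalized Wilcoxon test gives most weight to deaths that occur while many subjects are at risk, that is, early deaths. The condition for running it is an early difference in the same OS data. The feature that brings the test into the report is therefore the feature that makes it significant. Given the trigger, the statistic no longer follows the null distribution it is compared with. A better proportional-hazards test would not cure this.

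What is at stake is how a supportive p-value is read. If the log-rank test narrowly misses its boundary and a triggered Wilcoxon test gives p < 0.05, a reader would take that as support at the usual 5% level, which it is not. The situation is plausible. The protocol's amendment justification expects that subjects in the CCR arm may receive commercial enasidenib, which could dilute later differences and leave an early-separation pattern. That is a fair reason to want an early-weighted test, but it can be acted on in advance, without looking at the curves.

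**Working it through.** **Inputs from the documents.** Protocol 9.3 and SAP 4.4: 1:1 allocation, 316 subjects, 250 deaths, median OS 5.6 against 8 months (HR 0.7), drop-out about 9%, accrual 3 per month for 12 months and then 9 per month. SAP 12.2: interim at 65% of events, one-sided bounds 0.0055 and 0.0233.

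**Reproducing the plan's own figures.** The protocol states: "this design requires 250 deaths and 316 subjects (158 per treatment arm) to be randomized in order to achieve 80% power".
- Schoenfeld: d = 4(1.960 + 0.842)² / (ln 0.7)² = 31.4 / 0.1272 ≈ 247. Freedman's formula gives 253. The stated 250 lies between them.
- Power at 250 deaths with the interim at 163: 0.8005.
- Bounds as hazard ratios, exp(−2z/√d): the recomputed bounds give 0.6715 at 163 deaths and 0.7775 at 250, as stated.

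The documents give no error rate for the triggered Wilcoxon test, so it had to be simulated.

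**Method.** Both tests use Σ w_j (d_1j − e_1j) over death times, with w_j = 1 for the log-rank and w_j = number at risk for the Gehan form of the Wilcoxon. The quantity of interest is

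P(|Z_W| > 1.96 given trigger) = P(|Z_W| > 1.96 and trigger) / P(trigger).

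Null trials were generated on the plan's design: 20,000 per scenario, exponential OS with a common median of 5.6, 6.6 or 8 months, stopped at 250 deaths.

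**Assumptions the documents do not settle.** The proportional-hazards check was taken as any treatment-by-3-month-category term significant at 0.05, with 4, 5 or 7 intervals. Early separation was given a range of readings. Tests were unstratified and interval hazard ratios were score approximations.

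**Results under the SAP rule**

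| Reading of early separation, with the proportional-hazards check also rejecting | Wilcoxon rejection rate when used |
|---|---|
| Early HR below 1 | 7–9% |
| Early log HR larger in size than late, split at 3 months | 9–13% |
| Same, split at 6 months | 14–22% |
| Early HR beyond 0.8 by 6 months | 22–34% |
| Kaplan–Meier difference of at least 0.10 | 33–44% |
| Median across readings | 13–17% |
| No trigger, test always run | 4.7–5.1% |

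As an example, one null scenario with an absolute Kaplan–Meier difference of at least 0.05 at 6 months gave P(trigger) = 0.080 and P(trigger and reject) = 0.0123, so the conditional rate is 0.0123 / 0.080 = 15.4%. Rejections favouring AG-221 made up 8.0 of those 15.4 points, about half.

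Two repeat simulations with a categorical check, of 12,000 and 6,000 null trials, gave about 12–21% and 14–22%. In the second, the rate was 17.7% when the log-rank |z| up to 6 months exceeded the later |z|, 13.8% when the 3-month Kaplan–Meier difference exceeded 5 points, and 22.4% when both held.

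**Results under the protocol rule.** With a significant treatment-by-time interaction also required, the rates were about 10–66% (median 19–28%). With no such requirement, they were 8–9% for an early effect larger than the late one at 6 months, and 38–44% for a Kaplan–Meier difference of at least 0.10 at 6 months.

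**How often it would occur.** Across the assumed triggers, the test is both used and significant in about 0.3–2.0% of null trials. It is significant while the log-rank is not (two-sided p > 0.05) in about 0.2–1.2%; the repeat runs gave about 0.8% and 1.0%.

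**The case against.** The strongest reply is that nothing confirmatory rests on this test. Both documents call it a sensitivity analysis, and success on OS is decided by the log-rank boundary. The rule also makes a significant Wilcoxon result in a null trial rarer overall: 0.3–2.0% of trials, against about 5% if the test is always run. For the troublesome combination, a missed log-rank with a significant Wilcoxon, the 6,000-trial run gave 1.0% with the trigger and 2.2% when always reported (about 0.5% and 1.1% favouring AG-221). The thresholds used to simulate the trigger appear nowhere in the plan, and reading the test against its ordinary null is inferred from the general 0.05 rule.

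All of that stands, and it limits the consequence. It does not remove the problem. The p-value is seen only when the trigger has fired, and the rate that matters to its reader is then the conditional one, which exceeded 5% under every trigger tried. Always reporting the test raises the number of such results but gives them a known 5% meaning. The lack of a definition is a reason why no exact rate can be given, not a defence of the rule.

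Three stronger readings are tempting and are not supported.
- A reader might infer that the trial's Type I error for OS is inflated. It is not, since the Wilcoxon test enters neither the primary decision nor the alpha spending.
- A reader might infer a bias towards AG-221. The trigger has no stated direction, and early separation favouring CCR would fire it too. Restricted mean survival time and piecewise Cox regression are planned for any non-proportionality, including late separation.
- A reader might attach one rate to the SAP rule, for example the 38% that arises when a treatment-by-log-time interaction replaces the SAP's check and the early log-rank |z| exceeds the late one at a 6-month split. The SAP uses 3-month categories, and with those the same reading of early gives 17.7%.

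**Conclusion.** The concern holds for a supportive analysis. As written, the Wilcoxon test of OS is selected by the data feature to which it is most sensitive. When it is reported under no treatment effect, it rejects roughly 12–22% of the time under an assumed 3-month-category check with typical readings of early separation, and about 7–44% over a wider set of assumed triggers. Always run, it rejects about 5% of the time. The exact rate cannot be fixed because the trigger is undefined.

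The figures rest on exponential OS, unstratified tests, Gehan weights and a 0.05 level for the proportional-hazards check. Peto–Prentice weights gave mostly slightly lower rates with the same pattern. The stratified log-rank decision, the alpha spending and the OS–ORR–EFS sequence are unaffected, and the misleading combination arises in only about 1% of null trials. The change is worth making because it is nearly free and restores the meaning of the p-value.

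**What to change.** In SAP 10.2, delete the opening condition of item 4 (non-proportionality and early separation) and take the test out of the list that depends on the proportional-hazards result. In protocol 9.6.1, delete the matching clause about an early rather than late difference. State instead, for example: *A stratified generalized Wilcoxon test, with its weight function fixed in advance, will be reported as a sensitivity analysis of OS at the final analysis regardless of the shape of the curves or the proportional-hazards result. It does not replace the stratified log-rank test.*

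If the sponsor prefers to keep a trigger, it should at least be defined numerically and the resulting p-value labelled descriptive. That makes the rule explicit but does not restore the 5% rate.

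The cost is one sentence in the SAP, aligned protocol wording and one output, with no new data. The small downside is that the test is also reported when it is uninformative. Making restricted mean survival time and the piecewise hazard ratios unconditional is optional; no error rate was computed for them.
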